6.5. Extent of Exposure

Extent of exposure to GSK2857916 will be summarized.

The number of cycles administered to study treatment will be summarised with mean, median, standard deviation, minimum, and maximum.

Dose delivered per cycle (mg/kg/cycle) will be summarized using mean, median, standard deviation, minimum, and maximum by cycle and overall. The dose intensity (mg/kg/3 weeks), which is calculated as the cumulative actual dose (mg/kg) divided by expected duration of exposure in 3 weeks (last infusion date – first infusion date +

21)/21), will also be summarized. A by subject summary listing of data on exposure to all study treatments will be produced.

Dose reductions will be summarised by number of reductions and reasons for reductions. Dose delays will be summarised by number of delays, reasons for the delays, and delay duration (days). The number and percentage of the delays for intervals of 1-21, 22-42 and >42 days will be computed. Primary reasons for dose reductions and dose delays will also be summarized by cycle. Listing of all dose delays due to corneal events (GSK scale) and listing of dose delays and associated Eye Disorder Events (CTCAE) will be produced.

Duration of delays is defined as period from the expected start date of dose to actual start date of current dose. Calculation: (actual start date of current dose - expected start date of dose). Expected start date of dose = actual start date of previous dose + 21.

The summaries of dose modifications will be provided. All the dose reductions, dose escalations, infusion interruptions, incomplete infusions and dose delays will be listed. A plot showing the number and percentage of subjects treated at different dose levels over time will be provided.

The duration of exposure to study treatment (from first day to last day of treatment) will be calculated and summarized using mean, median, standard deviation, minimum, and maximum. A horizontal bar graph of duration of treatment will be produced that displays duration of treatment in months for each subject. Summary of duration of exposure by response category based on IRC will be presented.

A Kaplan Meier curve for time to treatment discontinuation by Response Category Based on IRC, and a Kaplan Meier curve for time to treatment discontinuation for subjects who have received at least 3 cycles of the study treatment will be presented.

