15.6.2. Study Population

Extent of Exposure

 • Number of days of exposure to study drug will be calculated based on the formula: Duration of Exposure in Days = min(Last infusionDate+20, Death date) – First infusion Date + 1 • Participants who were randomized but did not report a treatment start date will be categorised as having zero days of exposure. • The cumulative dose will be based on the formula: Cumulative Dose (mg/kg) = Sum of Dose at Each Cycle • Dose intensity will be calculated based on the formula: • Dose intensity (mg/kg/3 week) = Cumulative Dose/((last infusion date – first infusion date + 21)/21)

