	
end dates are not imputed, with the following exceptions for imputation of missing treatment end date at interim analyses.
 
 • For imputation of missing exposure end date at an interim analysis when subjects are still on treatment, the following conventions will be applied: 
 ○ If the missing end date is in the last exposure record, the earliest of: the date of the data cut-off, the date of withdrawal from the study, or the death date will be used ○ If the missing end date is not in the last exposure record, treatment start date for the record will be used • The imputed treatment end date will be used to calculate cumulative dose and duration of treatment as specified in Section 15.6.2 
If treatment end date is missing for a cycle, treatment start date for the cycle will be used.

PACT	
 • For PACT subjects, subject's last Visit date will be used as subject's end of study date, wherever required.

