Outcome of first occurrence [1] (n=xx)			
Resolved	XX (XX.X%)	XX (XX.X%)	XX (XX.X%)
re-started with dose delay and reduction	XX (XX.X%)	XX (XX.X%)	XX (XX.X%)
re-started with dose delay but no reduction	XX (XX.X%)	XX (XX.X%)	XX (XX.X%)
re-started with dose reduction but no delay	XX (XX.X%)	XX (XX.X%)	XX (XX.X%)
re-started without dose delay or reduction	XX (XX.X%)	XX (XX.X%)	XX (XX.X%)
not re-started	XX (XX.X%)	XX (XX.X%)	XX (XX.X%)
Not resolved, re-started	XX (XX.X%)	XX (XX.X%)	XX (XX.X%)

CONFIDENTIAL

205678

with dose delay and reduction	XX (XX.X%)	XX (XX.X%)	XX (XX.X%)
with dose delay but no reduction	XX (XX.X%)	XX (XX.X%)	XX (XX.X%)
with dose reduction but no delay	XX (XX.X%)	XX (XX.X%)	XX (XX.X%)
without dose delay or reduction	XX (XX.X%)	XX (XX.X%)	XX (XX.X%)
Not resolved, not re-started	XX (XX.X%)	XX (XX.X%)	XX (XX.X%)
not discontinued	XX (XX.X%)	XX (XX.X%)	XX (XX.X%)
discontinued, follow up ongoing	XX (XX.X%)	XX (XX.X%)	XX (XX.X%)
discontinued, follow up ended	XX (XX.X%)	XX (XX.X%)	XX (XX.X%)
Duration of first occurrence [1] [2]			
n	XX	XX	XX
Mean	XX.X	XX.X	XX.X
SD	XX.XX	XX.XX	XX.XX
Median	XX.X	XX.X	XX.X
Min.	XX	XX	XX
Max.	XX	XX	XX
Number of occurrences (based on subjects with the event)			
One	XX (XX.X%)	XX (XX.X%)	XX (XX.X%)
Two	XX (XX.X%)	XX (XX.X%)	XX (XX.X%)
Three or more	XX (XX.X%)	XX (XX.X%)	XX (XX.X%)
Outcome post treatment exposure			
Number of of subjects with unresolved Event at the end of treatment exposure, or with event onset post treatment exposure.	xx	xx	xx
Resolved	XX (XX.X%)	XX (XX.X%)	XX (XX.X%)
Not resolved, follow up ongoing	XX (XX.X%)	XX (XX.X%)	XX (XX.X%)

Not resolved, follow up ended	XX (XX.X%)	XX (XX.X%)	XX (XX.X%)
Time to resolution post treatment exposure, days			
n	XX	XX	XX
Mean	XX.X	XX.X	XX.X
SD	XX.XX	XX.XX	XX.XX
Median	XX.X	XX.X	XX.X
Min.	XX	XX	XX
Max.	XX	XX	XX

[1] The duration is defined as time from onset of any **blurred vision** event to the first time the subject is free of any such event. It requires at least one day gap between the resolution of all events from first occurrence to the onset of second occurrence.

[2] Imputed AE stop date was used in the calculation of duration if the outcome of the event was resolved/resolved with sequelae and AE stop date was partial with day missing. Imputed AE start date was used in the calculation if the start date was partial with day missing.

[3] The end of treatment exposure is defined as last infusion date +20 days.

Programming note:

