a. The event term (e.g. blurred vision) in footnote 1 need to be updated to be consistent with the title. b. Time to resolution post treatment exposure is calculated as (AE end date – end of treatment exposure) if there is unresolved event at the end of treatment exposure, or (first time the subject is free of any such event – onset date) if there is no unresolved event at the end of treatment exposure but with event onset post treatment exposure.

Example SAFE_T22
 Protocol: 205678
 Population: Full Safety

Table x.xxxx

Summary of Percentage of Duration of Exposure with Blurred Vision (CTCAE)

	2.5 mg/kg (N=97)	3.4 mg/kg (N=96)	3.4 mg/kg Lyo (N=25)

Percentage of Duration of Exposure			
n	48	31	11
Mean	52.9	46.8	42.8
SD	24.31	28.00	24.27
Median	55.4	51.2	48.8
Min.	2	2	5
Max.	95	89	75
Category of Percentage of Duration of Exposure			
n	48	31	11
>0 to <=20%	6 (13%)	8 (26%)	3 (27%)
> 20% to <= 40%	8 (17%)	6 (19%)	1 (9%)
> 40% to <= 60%	13 (27%)	4 (13%)	3 (27%)
> 60% to <= 80%	13 (27%)	9 (29%)	4 (36%)
> 80% to <= 100%	8 (17%)	4 (13%)	0

Note: n denotes the number of subjects with corneal events (CTCAE) of maximum grade ≥ 2 during exposure of study treatment.

Example: PRO_T1
 Protocol: 205678
 Population: ITT

Page 1 of 1
 (Data as of: 30MAY2001)

Table x.xxxx

Summary of Change in EORTC QLQ-C30/EORTC QLQ-MY20 Summary Score/Domain Scores from Baseline by Visit

summary score/domain score names (Physical Functioning, Role Functioning, etc)

Timepoint			Treatment Group A (N=xxx)	Treatment Group B (N=xxx)
Baseline	Actual Score	n	xxx	xxx
		Mean	x.x	x.x
		SD	x.xx	x.xx
		Median	x.x	x.x
		Min	x	X
		Max	xxx	xxx
Week 4	Actual Score	n	xxx	xxx
		Mean	x.x	x.x
		SD	x.xx	x.xx
		Median	x.x	x.x
		Min	x	x
		Max	xxx	xxx
	Change from Baseline	n	xxx	xxx
		Mean	x.x	x.x
		SD	x.xx	x.xx
		Median	x.x	x.x
		Min	x	x
		Max	xxx	xxx
Week x	Actual Score	n	xxx	xxx
		Mean	x.x	x.x
		SD	x.xx	x.xx
		Median	x.x	x.x
		Min	x	x
		Max	xxx	xxx
	Change from Baseline	n	xxx	xxx
		Mean	x.x	x.x
		SD	x.xx	x.xx
		Median	x.x	x.x
		Min	x	x
		Max	xxx	xxx

Example: PRO_T2
Protocol: 205678
Population: ITT

Page 1 of 1
(Data as of: 30MAY2001)

Table x.xxxx

Number (%) of patient with improvement in EORTC QLQ-C30EORTC QLQ-MY20 summary score/domain scores \geq 5/10/MID by visit

summary score/domain score names (Physical Functioning, Role Functioning, etc)

Timepoint		Treatment	Treatment
		Group A	Group B
		(N=xxx)	(N=xxx)
Week 4	N	xxx	xxx
	summary score/domain scores \geq 5/10/MID	xxx (xx%)	xxx (xx%)

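### Mock shell SAFE_T21 starts its post-exposure outcome rows at last infusion + 20 days without requiring that treatment was stopped, so participants on an open dose hold at the cut-off count as post-treatment outcomes

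*SAP*

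**What the plan says.** SAFE_T21 (SAP Section 15.14) is the layout for Tables 3.0200-3.0204, 3.0911 and 3.0912. Its lower part has a block on outcome after treatment exposure and a block on time to resolution after exposure.

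- **Start of the window:** "3] The end of treatment exposure is defined as last infusion date +20 days".
- **Who is counted:** "Number of of subjects with unresolved Event at the end of treatment exposure, or with event onset post treatment exposure".
- **Outcome rows:** resolved, unresolved with follow-up continuing, and "Not resolved, follow up ended".
- **Time to resolution:** programming note b says "Time to resolution post treatment exposure is calculated as (AE end date – end of treatment exposure) if there is unresolved event" at that date. For events that start later, it counts from onset.

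The first-occurrence block of the same shell does split unresolved, not re-started participants by treatment status. It has one row for those who have not discontinued, and separate rows for those who have, such as "discontinued, follow up ongoing".

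For PACT participants, Section 15.7.2.1 states only that the subject's "last Visit date will be used as" the end-of-study date. It does not say when their exposure ends.

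**The concern.** A block on outcome after treatment exposure will be read as describing what happens once the drug is stopped. As defined, it describes what happens more than 20 days after the most recent infusion recorded at the cut-off. The two coincide only for participants who have discontinued.

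The SAP expects participants for whom they differ. Section 6.5 tabulates delays of 22-42 and more than 42 days. Section 8.2.3 (item 15) and Table 3.12490 summarise eye-related delays still open at the data cut-off. Section 6.2 reports treatment as ongoing or discontinued.

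At stake are the percentage resolved and the time to resolution in these tables. Both would mix recovery after stopping with recovery, or non-recovery, during a hold, and the mixture would depend on the date of the cut-off.

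**Working it through.** **1. The 20-day offset is sound as an exposure measure.** Section 15.6.2 gives "Duration of Exposure in Days = min(Last infusionDate+20, Death date) – First infusion Date + 1". For k on-schedule cycles, last infusion − first infusion = 21(k − 1), so exposure = 21(k − 1) + 20 + 1 = 21k. That is 21, 63 and 105 days for k = 1, 3 and 5. The dose-intensity denominator in the same section, last − first + 21, gives the same values. The offset is not the problem.

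**2. Where the boundary falls at the cut-off.** Let d be the days from last infusion to cut-off. Days past the boundary = d − 20. Section 6.5 sets "Expected start date of dose = actual start date of previous dose + 21", so a delay of x days means d = 21 + x.

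| Status at cut-off | d | Days past boundary |
|---|---|---|
| On schedule | 10 | −10 |
| On schedule, day before next dose | 20 | 0 |
| Open delay of 1 day | 22 | 2 |
| Open delay of 21 days | 42 | 22 |
| Open delay of 42 days | 63 | 43 |
| Open delay of 63 days | 84 | 64 |

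Every open delay is past the boundary although treatment has not been stopped. On-schedule participants have not passed it.

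**3. One participant at different cut-offs.** Take an event unresolved on day 20 after the last infusion that resolves on day 50, with dosing restarted on day 63.

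- Cut-off after day 20 but before day 50: counted as unresolved, follow-up continuing.
- Cut-off from day 50 until the restart: counted as resolved, with time to resolution 50 − 20 = 30 days.
- Cut-off after the restart: the boundary moves to 63 + 20 = day 83. The event ended before then and leaves the block. The participant re-enters only with an event unresolved at, or starting after, the new boundary.

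The clinical course is the same in all three cases; only the cut-off differs.

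**4. Possible effect on the resolved percentage.** The SAP gives no counts, so these are assumed: 40 discontinued participants in the block, of whom 20 resolve. Add a participants on hold who recovered and b on hold who did not. Reported percentage = (20 + a) / (40 + a + b).

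| a | b | Reported resolved |
|---|---|---|
| 0 | 0 | 20/40 = 50.0% |
| 0 | 5 | 20/45 = 44.4% |
| 0 | 10 | 20/50 = 40.0% |
| 5 | 0 | 25/45 = 55.6% |
| 5 | 5 | 25/50 = 50.0% |

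The shift can be down, up or nil.

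**The case against.** The case against giving this weight is substantial, and most of it stands.

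- **Participants dosed on schedule.** A reader might infer that everyone still on treatment with an ongoing event is counted as a post-treatment failure. The wording does not support that. Their boundary falls on or after the cut-off, so they are not plainly unresolved at that date. Their status is undefined.
- **PACT.** A reader might infer that these participants are entered as unresolved with follow-up ended. The SAP sets only an end-of-study date for them and says nothing about how their ongoing events are classified.
- **SAFE_T4a.** This shell might be cited as using a better clock. It measures time from the same last dose + 20 days. It differs only in selecting participants by their status at the end-of-treatment visit.
- **Reversibility is analysed elsewhere.** Section 8.5 item 2, Tables 3.0410 and 3.0420, and Figures 3.53010 and 3.53020 address recovery from the end-of-treatment visit or after discontinuation. The SAFE_T21 rows are not the only evidence on it.
- **Dose groups.** Nothing in the SAP shows that the share of participants on open hold differs between arms, so a biased dose comparison cannot be claimed.
- **Narrow group and timing.** To count as resolved during a hold, an event must be unresolved at day 20, resolve later, and precede any re-dosing by the cut-off. Sections 9 and 12.2 already describe primary-analysis work in the past tense. Tables 3.0200, 3.0203 and 3.0204 are listed for the primary analysis only.

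None of this removes the open-hold case, which follows directly from the footnote and the denominator row.

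**Conclusion.** The point holds, as a minor one. SAFE_T21 applies a post-treatment label to a window that does not require treatment to have ended. It therefore counts participants on an open hold past day 20 as post-treatment outcomes, and whether they are counted changes with the cut-off date. For on-schedule and PACT participants the rule is unclear rather than demonstrably wrong.

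The size and net direction of the effect are unknown; the percentages above rest on assumed counts. Only descriptive ocular tables are touched: 3.0200-3.0204, 3.0911 and 3.0912, of which 3.0201, 3.0202, 3.0911 and 3.0912 are also due at end of study. The primary response-rate analysis is unaffected.

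**What to change.** In SAFE_T21, limit the post-exposure outcome rows and the post-exposure time-to-resolution rows to participants with a recorded permanent discontinuation of study treatment by the data cut-off. The last infusion + 20 days clock can stay.

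Add a separate row for treatment not discontinued. It should hold participants with an ongoing or hold-period event who have not stopped, including those moving to PACT. This matches the split already made in the first-occurrence block.

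The later tables of the same Characteristics II type (for example 3.12770-3.12772 and 3.60100) refer to external reporting efforts. Their rule cannot be seen in the SAP, so check them for it rather than assume that they share it.

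The cost is one footnote condition and one row, using discontinuation data that Section 6.2 already summarises. The post-treatment n becomes smaller. If the primary-analysis tables used the present rule, their figures will not be directly comparable with the end-of-study versions unless they are rerun.
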